## 6.3 CONCOMITANT MEDICATIONS

For this protocol, a prescription medication is defined as a medication that can be prescribed only by a properly authorized/licensed clinician. Medications to be reported in the Case Report Form (CRF) are concomitant prescription medications, over-the-counter medications and supplements.

Medication usage will be documented for medications subject is currently taking at time of Screening Visit, for any medication usage stopped within the previous thirty (30) days, and for medication changes (started, stopped, or change of dose/frequency) through study exit. Medications usage, both prescription and over-the-counter, for the following indications and/or systems will be documented in the Concomitant Medication Log for each subject:

- Allergies
- Nasal, Ear and Throat
- Asthma
- Migraines
- Blood thinners/anti-coagulants

Medications taken in conjunction with time of treatment or post-treatment for pain or anxiety, both prescription and over-the-counter, pain or discomfort will be documented.

Additionally, any medication that is determined by the Investigator to be a potential safety issue or concern, and/or any medication taken in connection with treatment for an Adverse Event will be documented.

Subjects will refrain from the use of ipratropium bromide (i.e. Atrovent) at least 3 days prior to treatment and through the 3-Month timepoint.

At the Investigator's discretion, subjects that have an active coagulation disorder or are receiving anti-coagulants, may be asked to temporarily stop usage prior to treatment.

## 7 STUDY INTERVENTION DISCONTINUATION AND PARTICIPANT DISCONTINUATION/WITHDRAWAL

### 7.1 PARTICIPANT DISCONTINUATION/WITHDRAWAL FROM THE STUDY

Participants are free to withdraw from participation in the study at any time upon request.

An investigator may discontinue or withdraw a participant from the study for the following reasons:

- Significant study non-compliance
- If any clinical adverse event (AE), laboratory abnormality, or other medical condition or situation occurs such that continued participation in the study would not be in the best interest of the participant
- If the participant meets an exclusion criterion (either newly developed or not previously recognized) that precludes further study participation

The reason for participant discontinuation or withdrawal from the study will be recorded on the Study Exit Case Report Form (CRF). Subjects who sign the informed consent form but do not receive the study treatment may be replaced. Subjects who sign the informed consent form and receive the study treatment, and subsequently withdraw, or are withdrawn or discontinued from the study, may be replaced at the discretion of the Sponsor.

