**Figure 2. ClariFix™ Device**

## 2.5 RISK/BENEFIT ASSESSMENT

### 2.5.1 KNOWN POTENTIAL RISKS

The study cryotherapy procedure involves transnasal placement of the ClariFix device under endoscopic visualization and use of local anesthesia. In order to minimize risks associated with the study, the procedure will be performed by practicing otolaryngologists experienced in transnasal procedures. Further, subjects with known allergies to local anesthetic agents shall be excluded from participation in the study.

While nasal endoscopy is generally known to be safe, anticipated risks may include, but are not limited to:

- Temporary pain, discomfort or irritation
- Bleeding
- Cerebrospinal fluid (CSF) leak

Similarly, while generally known to be safe, submucosal placement of a needle and delivery of local anesthesia may be additionally associated with the following risks, not limited to:

- Minor bleeding
- Pain with injection
- Facial numbness or tingling
- Sedation
- Tachycardia, nervousness, anxiety
- Lightheadedness, dizziness, confusion,
- Muscular twitching, tremors
- Infection
- Allergic reaction
- Lidocaine or Tetracaine toxicity with overdose
- Visual disturbance
- Vomiting
- Headache
- Tinnitus
- Seizures
- Hypotension, bradycardia
- Unconsciousness
- Respiratory arrest
- Cardiac arrest

While generally considered safe, cryotherapy has known potential risks including, but not limited to:

- Postoperative bleeding
- Epistaxis
- Nasal obstruction
- Nasal crusting
- Ear blockage

In addition, the specific nature of cryosurgery using the ClariFix Device results in a known potential for adverse events related to the cold application. Potential risks and complications are outlined in the IFU (See Appendix I).

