### 5.2 EXCLUSION CRITERIA

An individual who meets any of the following criteria will be excluded from participation in this study:

1. Subject has clinically significant anatomic obstructions that limit access to the posterior nose including severe septal deviation, nasal polyps, and sinonasal tumor.
2. Subject has had prior sinus or nasal surgery that significantly alters the anatomy of the posterior nose.
3. Subject has moderate to severe ocular symptoms as determined.
4. Subject has a history of epistaxis in the past 3 months.
5. Subject has a history of rhinitis medicamentosa.
6. Subject has had prior head or neck irradiation.
7. Subject has active or chronic nasal or sinus infection.
8. Subject is pregnant.
9. Subject has an allergy or intolerance to anesthetic agent.
10. Subjects with cryoglobulinemia, paroxysmal cold hemoglobinuria, cold urticaria, Raynaud's disease, and/or, open and/or infected wounds at or near the target tissue.
11. Subject is currently participating in another clinical research study.
12. Subject has any physical condition that, in the investigator's opinion, would prevent adequate study participation or pose increased risk.

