#### 8.4.6 TIME PERIOD AND FREQUENCY FOR EVENT ASSESSMENT AND FOLLOW-UP

The occurrence of an adverse event (AE), adverse device effect (ADE) or serious adverse event (SAE) may come to the attention of study personnel during study visits and interviews of a study participant presenting for medical care, or upon review by a study monitor.

Information to be collected includes event description, time of onset, clinician's assessment of severity, relationship to study product (assessed only by those with the training and authority to make a diagnosis), and time of resolution/stabilization of the event. All AEs occurring while on study must be documented appropriately regardless of relationship. All AEs will be followed to adequate resolution.

Any medical condition that is present at the time that the participant is screened will be considered as baseline and not reported as an AE. However, if the study participant's condition deteriorates at any time during the study, it may be recorded as an AE.

Changes in the severity of an AE will be documented to allow an assessment of the duration of the event at each level of severity to be performed. AEs characterized as intermittent require documentation of onset and duration of each episode.

Study site will record all reportable events with start dates occurring any time from treatment with the study device until 7 (for non-serious AEs) or 30 days (for SAEs) after the last day of study participation. At each study visit, the investigator will inquire about the occurrence of AE/SAEs since the last visit. Events will be followed for outcome information until resolution or stabilization.]

---

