PRO	Patient-reported outcome
rTNSS	Reflective Total Nasal Symptom Score
SAE	Serious adverse event
SAP	Statistical analysis plan
SAS®	Statistical analysis software
SD	Standard deviation
SNOT-22	22-Item Sino-Nasal Outcome Test
VAS	Visual analog scale

2 Introduction

This statistical analysis plan (SAP) contains the definitions of analysis sets, derived variables, and statistical methods for the analyses of efficacy and safety data from the study entitled, “*Feasibility Study of Multi-Treatment Posterior Nasal Nerve Modulation for Treatment of Chronic Rhinitis*”. This is a prospective, multicenter, open-label, feasibility study (Arrinex Clinical Investigational Protocol #CT-0005). Participants will be consented and enrolled before study procedures. All participants who receive treatment will be assessed through the 90-day follow-up.

3 Study Design

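### Investigator withdrawal after the single Day 0 treatment (Protocol 7.1) can end safety follow-up before Day 90, and neither document keeps the participant under AE/SAE review

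*Protocol*

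**What the plan says.** Protocol 7.1 gives the investigator discretionary grounds to take a participant out of the study. One is an adverse event or other condition "such that continued participation in the study would not be in the best interest of the participant". Another reads "If the participant meets an exclusion criterion (either newly developed or not previously recognized) that precludes further study participation". Neither ground is confined to the time before treatment. The same section provides for participants who have been treated and then leave, "or are withdrawn or discontinued from the study, may be replaced at the discretion of the Sponsor".

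Two of the exclusion criteria in Protocol 5.2 read "Subject has a history of epistaxis in the past 3 months" and "Subject has active or chronic nasal or sinus infection". Protocol 2.5.1, in the list that opens "While generally considered safe, cryotherapy has known potential risks", names epistaxis and postoperative bleeding.

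On duration of follow-up, SAP 2 states: "All participants who receive treatment will be assessed through the 90-day follow-up". SAP 4.1 nevertheless lists withdrawal by the physician or sponsor for health or welfare among the reasons for leaving before Day 90. Protocol 8.4.6 has sites record new events "until 7 (for non-serious AEs) or 30 days (for SAEs) after the last day of study participation", and follows events already known until they resolve or stabilize.

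On analysis, the safety population is everyone treated (Protocol 9.3, SAP 4.3 and 8.1). SAP 10.4 plans no missing-data or sensitivity analysis.

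**The concern.** Cryoablation is given once, at Visit 3. After that there is no study treatment to stop, so withdrawing a participant from the study does nothing except shorten observation. Yet entry criteria written to decide who should be treated are carried over, unedited, as possible grounds for exit after treatment. For epistaxis, the criterion also describes something the procedure is known to cause.

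The primary endpoint is the incidence of procedure-related SAEs and/or SADEs. A participant who has a non-serious complication, is withdrawn because of it, and later has a separate SAE that nobody records will stay in the denominator and count as SAE-free. In a study of 30 whose main output is a safety proportion, a single such case changes the result.

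**Working it through.** **Inputs.** Treatment on Day 0 (Protocol 1.3, 6.1 and 8.1.3). Final visit on Day 90 ± 14, so between Day 76 and Day 104 (Protocol 8.1.6). New-event recording for 7 days (non-serious AEs) or 30 days (SAEs) after the last day of participation (Protocol 8.4.6). Thirty treated participants (SAP 3.1.3), a convenience sample with no calculation to reproduce.

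**Step 1: when capture ends.** For a participant whose last day is *d*, capture of new events ends on *d* + 7 (AE) and *d* + 30 (SAE). The same rule applies to completers.

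| Last day of participation | AE capture ends | SAE capture ends |
|---|---|---|
| Withdrawn, Day 7 | 7 + 7 = 14 | 7 + 30 = 37 |
| Withdrawn, Day 30 | 30 + 7 = 37 | 30 + 30 = 60 |
| Completes, Day 76 | 76 + 7 = 83 | 76 + 30 = 106 |
| Completes, Day 90 | 90 + 7 = 97 | 90 + 30 = 120 |

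The extension cancels in the comparison, so the shortfall is the completion day minus the exit day for both event types. For exit on Day 7:

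- Against a Day 90 completer: 97 − 14 = 83 and 120 − 37 = 83 days.
- Against a Day 76 completer: 83 − 14 = 69 and 106 − 37 = 69 days.

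Capture reaches Day 90 only if exit is on or after Day 60 for SAEs (90 − 30) or Day 83 for non-serious AEs (90 − 7).

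**Step 2: what each endpoint can lose.**

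- *Primary SAE/SADE incidence.* If the trigger was itself a procedure-related SAE, the participant is already a case. If it was not, a separate new SAE starting more than 30 days after exit can go unrecorded.
- *Participants with any related AE (secondary).* If the trigger was related, the participant is already a case and nothing changes. If it was unrelated, a later related AE can be missed.
- *Event totals (SAP 8.2.1 and 8.2.2) and worst severity per participant (Protocol 9.4.4).* These can be understated whatever the trigger was.
- *rTNSS, endoscopy and questionnaires.* Remaining Day 30 and Day 90 values are lost. Analyses use available data without imputation (Protocol 9.4.1).

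**Step 3: size for the primary endpoint.** Exact (Clopper–Pearson) two-sided 95% limits, with event counts assumed for illustration:

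- 0/30: upper limit 1 − 0.025^(1/30) = 11.6%, so 0% (0 to 11.6%).
- 1/30: 3.3%. Lower limit 1 − 0.975^(1/30) = 0.1%. Upper limit, the 97.5th percentile of Beta(2, 29), is 17.2%.

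One unrecorded SAE therefore moves the estimate by 3.3 percentage points and the upper limit by 17.2 − 11.6 = 5.6 points.

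**Step 4: how often.** The documents do not allow an estimate. In the 27-participant pilot, the 3 who missed 90 days were lost to follow-up. In the 100-participant study, 2 had exited by that point, with no reasons given (Protocol 2.3).

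**The case against.** The strongest reply is that the plan, read as a whole, leans towards observing complications. Withdrawal is optional and qualified, and a nosebleed hardly precludes an office visit or a questionnaire. Eligibility is checked only at Visits 1 and 2 (Protocol 1.3). After treatment, a complication can prompt an added exam at Visit 4 or an unscheduled visit, and known events are followed until they settle. SAP 4.1 lists every early discontinuation with its reason. The loss to the primary endpoint needs a specific sequence: exit for something other than a related SAE, then a separate procedure-related SAE more than 30 days later. That is a narrow path after a one-time office procedure.

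Most of this stands, and it rules out several stronger readings that a reader might infer:

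- *Any adverse event permits withdrawal.* It does not; the best-interest condition applies.
- *Complication cases disappear from the safety results.* They do not. The trigger is recorded, followed and counted, so related-AE incidence is not lowered when the trigger was related.
- *Efficacy is biased upward.* Nothing in the documents links these complications to worse symptom change. The direction is unknown.
- *Infection and wounds are listed cryotherapy risks too.* Protocol 2.5.1 puts infection under local anaesthesia and does not name open wounds. The IFU list is not in the text available. Epistaxis is the clear overlap.
- *A Day 7 exit loses 76 AE days and 53 SAE days against a completer.* Those are the distances from Day 14 and Day 37 to Day 90. They leave out the completer's own 7- and 30-day extension and the ± 14-day window.

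What the reply does not supply is a sentence keeping a withdrawn, treated participant under safety review. The qualifier about precluding participation is undefined once the only treatment has been given. Events are asked about at study visits, no contact is scheduled after exit, and unscheduled visits stop when participation ends (Protocol 8.1.7). Listing exits discloses the gap but does not recover the data.

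**Conclusion.** The point holds in a limited form. Protocol 7.1 permits, at the investigator's discretion and under stated conditions, a post-treatment withdrawal that can only end observation. At least one possible ground, epistaxis, is a known effect of the procedure. SAP 2 promises 90-day assessment of everyone treated, while Protocol 7.1, Protocol 8.4.6 and SAP 4.1 together allow less.

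The exposure is to late, separate events and to the remaining scheduled assessments, not to the event that triggered the exit. For exit on Day 7 the shortfall is 83 days of new-event capture against a Day 90 completer, or 69 against a Day 76 completer. For the primary endpoint, one missed SAE is the difference between 0/30 and 1/30. This assumes that at least one such exit and one such late SAE occur; the frequency of either is unknown, so no expected bias can be stated. It is worth correcting because the safety proportion is the study's primary result, the sample is small and the change is cheap.

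**What to change.** Leave the investigator's discretion to stop study assessments as it is, and separate it from safety follow-up:

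1. In Protocol 7.1 and 8.4.6, state that any treated participant withdrawn by the investigator or sponsor continues AE/SAE review, by visit or other contact, to Day 90. Any questionnaires the participant finds acceptable continue too. The exceptions are withdrawal of consent, loss of contact and death.
2. State whether the 7- and 30-day extension then runs from Day 90. If it does, a withdrawn participant is covered to Day 97 and Day 120, like a Day 90 completer.
3. In the SAP, report the number of treated participants with incomplete safety follow-up, with the last day observed, beside the primary result. Include any who were replaced.
4. Reconcile Protocol 7.1 and 8.4.6 with SAP 2 and 4.1, so that all four describe the same follow-up for a treated participant who is withdrawn.

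The cost is a short protocol amendment, a few lines in the SAP, and a few extra contacts on a visit schedule that already exists. These changes concern data collection only and set no clinical withdrawal rule.

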### 7.2 LOST TO FOLLOW-UP

A participant will be considered lost to follow-up if he or she fails to return for 2 or more scheduled visits and is unable to be contacted by the study site staff.

The following actions must be taken if a participant fails to return to the clinic for a required study visit:

- The site will attempt to contact the participant and reschedule the missed visit and counsel the participant on the importance of maintaining the assigned visit schedule and ascertain if the participant wishes to and/or should continue in the study.
- Before a participant is deemed lost to follow-up, the investigator or designee will make every effort to regain contact with the participant (where possible, 3 telephone calls and, if necessary, a certified letter to the participant's last known mailing address or local equivalent methods). These contact attempts should be documented in the participant's medical record or study file.

- Should the participant continue to be unreachable, he or she will be considered to have withdrawn from the study with a primary reason of lost to follow-up.

## 8 STUDY ASSESSMENTS AND PROCEDURES

### 8.1 STUDY PROCEDURES

#### 8.1.1 SCREENING VISIT (VISIT 1) (DAY -30 TO 0)

Potential study subjects will be pre-screened against study eligibility criteria. Those individuals, that meet pre-screening criteria will be offered participation in the study and will be consented (see Section 10.1.1).

The Screening Visit may occur in-office up to 30 days prior to the Treatment Visit (Visit 1). Visit 1 may occur on the same day as the Baseline (Visit 2) and Treatment (Visit 3) Visits.

After obtaining informed consent, the following study activities will be completed:

1. Subject to complete Subject Demographics Questionnaire (See Addendum: Patient Questionnaires). Data collected includes month and year of birth, biological gender, ethnicity and race.
2. Subject will complete rTNSS questionnaire (see Section 8.2.1).
3. Concomitant Medications will be documented (see Section 6.3).
4. Relevant Medical History will be documented. This will include, but not limited to, the following:
  - a. History of nasal symptoms including rhinitis, epistaxis and sinusitis;
  - b. History of facial pain, TMJ, ocular symptoms, and ear/nose complaints;
  - c. Prior allergy testing; and
  - d. History of rhinitis medication usage and response to treatment.
5. Physician will complete a Physical Nasal Exam (see Section 8.3.1) and document findings.
6. Investigator will review Inclusion/Exclusion criteria, and subjects meeting criteria will be scheduled for the Baseline Visit (Visit 2).

**Note:** Due to post-market, on-label use of device, pregnancy exclusion will be based upon self-report. Pregnancy testing will not be required to confirm eligibility.

#### 8.1.2 BASELINE VISIT (VISIT 2) (DAY -7 TO 0)

Subjects meeting eligibility criteria will return in-office for the Baseline Visit (Visit 2). The Baseline Visit may be completed the same calendar day as the Screening (Visit 1) and Treatment (Visit 3) Visits, however it must be completed no earlier than seven (7) calendar days prior to the Visit V3.

At Visit 2, the following study activities will be completed:

1. Subject will complete rTNSS questionnaire.

**Note:** If Visit 2 is completed the same calendar day as Visit 1, second rTNSS is not to be completed.
2. Concomitant Medication usage will be updated.

3. Eligibility Criteria will be confirmed.
  - a. Subjects meeting criteria will be considered enrolled and continue Visit 2 activities.
  - b. Subjects not meeting criteria will be considered a Screen Failure and their study participation will be complete.
4. Subject will complete the NOSE (see Section 8.2.2), SNOT-22 (see Section 8.2.3), VAS for Nasal Symptoms (see Section 8.2.5), and MiniRQLQ (see Section 8.2.4).

Treatment Visit, if on another day, should be confirmed with the Subject.

Additionally, for subjects that do not have confirmation of a prior allergy test within the last 10 years, they will be scheduled for allergy testing prior to study exit.

---

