#### 8.1.5 1-MONTH FOLLOW-UP VISIT (VISIT 5) (DAY 30)

Subjects will return to the office at thirty (30) days ( $\pm 7$  days) from Visit 3 for the 1-Month Follow-up Visit (Visit 5).

At Visit 5, the following study activities will be completed:

1. Subject will complete rTNSS, NOSE, SNOT-22, VAS for Nasal Symptoms and MiniRQLQ questionnaires.
2. Concomitant Medication usage will be updated.
3. Subject will be assessed for any new Adverse Events experienced since Visit 4 and/or review of previously unresolved Adverse Events.
4. Physician will complete Physical Nasal Exam and document findings.
5. Investigator will complete Clinical Global Impression—Improvement (CGI-I) scale (see Section 8.2.5).
6. Subject will be schedule for 3-Month Follow-up visit (Visit 6).

---

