#### 8.2.6 CLINICAL GLOBAL IMPRESSION – IMPROVEMENT (CGI-I)

The Clinical Global Impression--Improvement (CGI-I) rating scales is a clinician completed subject assessment of the changes of symptoms since time of treatment based on their clinical experience. The CGI-I is a 7-point Likert scale that ranges from a scale of 1 being "Very Much Improved" to 7 being "Very Much Worse".

The CGI-I will be completed that the 1- (V5) and 3-Month (V6) Follow-up Visits at the completion of the Physical Nasal Exam (See Section 8.3.1). Additionally, the CGI-I may, at the discretion of the clinician, be administered at an Unscheduled Visit (See Section 8.1.7).

---

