#### 8.3.1 PHYSICAL NASAL EXAM

A physical nasal evaluation of the treatment area and nasal cavity will be performed by a licensed clinician via endoscope at the Screening (Visit 1), 1-Week (Visit 4 due to AE occurrence or monitoring), 1-Month (Visit 5) and 3-Month (Visit 6).

**IMPORTANT:** Except for 1-Week (Visit 4), if applicable, subjects are not to be decongested prior to the Physical Nasal Exam.

Prior to decongestant, bilateral endoscopic videos or images are to be collected capturing the head of the inferior and middle turbinates (see Section 8.3.3).

The clinician will assess each side of the nasal cavity for hypertrophy of the middle and inferior turbinates and congestion using a 0 to 3 scale (0=None, 1=Mild, 2=Moderate, or 3=Severe).

After decongestant, a second bilateral endoscopic videos or images are to be collected capturing the head of the inferior and middle turbinates.

At Visit 4 (if applicable), Visit 5 and Visit 6, the clinician will assess each treatment area (left middle meatus, left inferior meatus, right middle meatus and right inferior meatus) for bleeding, crusting, and swelling using the same scale of 0 to 3.

An endoscopic exam may be completed at an Unscheduled Visit at the discretion of the Investigator, in the event of a study-related adverse event.

---

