7.2.3 Quantitative nasal endoscopy scores

Endoscopic nasal examinations (before and after decongestant administration) will be performed at baseline and at the 30-day and 90-day follow-up visits. Photos will be taken of the middle and inferior turbinates (before and after decongestant). After deidentification and randomization, an independent physician, blinded to the participant and study visit, will review and grade each photo for 3 findings (inferior turbinate hypertrophy, middle turbinate hypertrophy, and nasal congestion). Each finding will be rated on a scale from 0 (none) to 3 (severe).³ Predecongestant and postdecongestant scores for each finding will be summarized using counts and percentages at baseline and the at the 30-day and 90-day visits.

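### When Visits 1 and 2 share a day and the listed steps are followed, baseline NOSE, SNOT-22, VAS and MiniRQLQ come after the decongestant, whereas the follow-up questionnaires come before it

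*Protocol*

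**What the plan says.** Protocol 8.1.1 permits a combined visit: "Visit 1 may occur on the same day as the Baseline (Visit 2) and Treatment (Visit 3) Visits". At step 5 of Visit 1, "Physician will complete a Physical Nasal Exam (see Section 8.3.1) and document findings"; the review of eligibility follows at step 6.

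Protocol 8.3.1 describes that exam. Images and gradings are taken undecongested, and then "After decongestant, a second bilateral endoscopic videos or images are to be collected capturing the head of the inferior and middle turbinates". SAP 7.2.3 agrees: "Endoscopic nasal examinations (before and after decongestant administration) will be performed at baseline and at the 30-day and 90-day follow-up visits". The Schedule of Activities (Protocol 1.3) has no nasal exam at Visit 2, so the SAP's baseline exam is the one at Visit 1.

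Protocol 8.1.2 confirms eligibility at step 3, and only participants who meet the criteria go on with the visit. Step 4 then begins "Subject will complete the NOSE (see Section 8.2.2), SNOT-22 (see Section 8.2.3" and continues with the VAS and the MiniRQLQ.

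At the 1-month visit (Protocol 8.1.5) step 1 is "Subject will complete rTNSS, NOSE, SNOT-22, VAS for Nasal Symptoms and MiniRQLQ questionnaires", and the exam is step 4. Protocol 8.1.6 gives the same order at 3 months.

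**The concern.** The trial has a single arm, so its evidence on efficacy is each participant's change from baseline. Both ends of that change should be collected under the same conditions. For NOSE, SNOT-22, VAS and MiniRQLQ the listed order gives a same-day participant a baseline questionnaire after decongestion and follow-up questionnaires before it. Participants whose Visit 2 falls on a separate day have no such mismatch, so the condition at baseline can vary with how a site schedules its visits.

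The stake is modest. SAP 3.1.1 treats these four instruments as exploratory. Protocol 9.4.3 lists them as secondary, however, and Protocol 9.4.2 says a secondary endpoint may become primary in the next study. Avoidable noise or bias in their baselines weakens that use. The analysis would not show it either, since SAP 10.4 and 10.6 plan no sensitivity or subgroup analyses.

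**Working it through.** The plan gives no figure to reproduce, because the question is one of order. The steps compare as follows.

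| Occasion | Exam with decongestant | Four questionnaires | Order as listed |
|---|---|---|---|
| Visits 1 and 2 on the same day (8.1.1, 8.1.2) | Visit 1, step 5 | Visit 2, step 4 | After decongestant |
| Visit 2 on a separate day (8.1.2, 1.3) | None at Visit 2 | Visit 2, step 4 | No decongestant that visit |
| Visit 5 (8.1.5) | Step 4 | Step 1 | Before decongestant |
| Visit 6 (8.1.6) | Step 4 | Step 1 | Before decongestant |

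**Does another rule prevent this?** The only timing rule on decongestion, in Protocol 8.3.1, keeps the nose undecongested before the exam. It protects the exam findings and does not mention the questionnaires.

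**Is rTNSS affected?** No. It is step 2 of Visit 1, ahead of the exam. It is not repeated when Visit 2 falls on the same day, and it is step 1 at Visits 5 and 6.

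**What period do the four instruments cover?** NOSE covers the past month (8.2.2), SNOT-22 two weeks (8.2.3), MiniRQLQ one week (8.2.4) and VAS one week (8.2.5). A decongestant given shortly beforehand does not alter that period. It can act only by colouring how the participant recalls it. NOSE and SNOT-22 are described as asking about current symptoms over the window, which leaves some room for this.

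**Direction.** All four score higher for worse symptoms, and Protocol 9.4.1 defines change as visit value minus baseline value. If relief at that moment lowers a participant's baseline by d, the recorded change is

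visit − (baseline − d) = (visit − baseline) + d.

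Improvement is a negative change, so adding d understates it.

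**Size.** With a share p of same-day participants and an average shift d among them, the mean change moves by p × d. The documents give neither quantity. The number affected could be anywhere from 0 to 30 of the planned 30, and nothing in the plan supports a value for d, so no numerical estimate is offered.

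**The case against.** The strongest reply is that these questionnaires ask about weeks, not minutes. This stands in large part. A reader might infer that baseline and follow-up measure the nose in two different states, or that same-day and separate-day participants cannot be compared. The recall windows do not support either reading. What remains is a difference in the conditions under which the forms are completed. Much of SNOT-22 and MiniRQLQ also concerns daily life, where an effect of brief nasal relief is less plausible.

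A second reply is that the protocol nowhere makes the list order binding. That is correct, and the point is conditional for that reason. The order is still more than numbering. Enrolment is decided before the questionnaires are given, and an exclusion such as anatomic obstruction of the posterior nose (5.2, criterion 1) naturally rests on the exam. A site that follows the text would arrive at this sequence.

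A third reply is that little depends on it. The primary endpoint is safety, rTNSS is spared, and the likely bias is against the device. This stands, and it limits the severity.

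A reader might also extend the point to CGI-I, which is scored at the "Follow-up Visits at the completion of the Physical Nasal Exam" and so after the decongestant. The documents do not support that. CGI-I has no baseline score to mismatch, its timing is the same at both follow-up visits, and SAP 7.3.5 reports it as category counts. The Visit 1 exam also includes a decongestant. Moving CGI-I would be a matter of preference.

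**Conclusion.** The point holds in a limited form. On a combined Visit 1 and Visit 2, with the steps followed as listed, the baseline NOSE, SNOT-22, VAS and MiniRQLQ are completed after a decongestant. At Visits 5 and 6, and at a separate-day Visit 2, they are completed without prior decongestion. This could colour recall at baseline and would then most likely understate improvement.

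The conclusion rests on two assumptions: that sites keep to the listed order, and that some participants have same-day visits. The size of any shift and the share affected are unknown. Safety and rTNSS are untouched. Severity is minor, and the change is worth making because it removes an avoidable asymmetry at almost no cost.

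**What to change.** In Protocol 8.1.1 and 8.1.2, state that when Visits 1 and 2 fall on the same day, NOSE, SNOT-22, VAS and MiniRQLQ are completed after consent and before any decongestant, together with the Visit 1 rTNSS. Add that these responses are not used if the participant proves to be a screen failure.

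This re-orders existing steps and adds no assessment. The one cost is that a few screen failures will complete questionnaires that are not used.
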